APPENDIX 1. Severity grading of papulopustular rosacea, adapted from Sanchez *et al.*, 2005.

Severity	Papules/Pustules	Study Score
Mild	1-9	1
Moderate	10-14	2
Severe	15+	3

APPENDIX 2. Clinical score for assessing rosacea severity, reproduced from Sanchez *et al.*, 2005.

Table I. Clinician's Global Severity Score*

Score/Grade	Definition	Guideline
(0) None to very mild	No signs or symptoms present; at most, mild erythema	0-3 papules/pustules Erythema Assessment Score Total score <1; Area-specific score: 0 or 1
(1) Mild	Mild erythema present; none to few papules/pustules	4-9 papules/pustules Erythema Assessment Score Total score <5; Area-specific score: 0 or 1
(2) Moderate	Moderate erythema; moderate number of papules/pustules	10-14 papules/pustules Erythema Assessment Score Total score 6-10; Area-specific score: 2 or 3
(3) Severe	Severe erythema; papules/pustules common	15-19 papules/pustules Erythema Assessment Score Total score 16-20; Area-specific score: 3 or 4
(4) Very severe	Fiery red erythema; numerous papules/pustules	>20 papules/pustules Erythema Assessment Score Total score 16-20; Area-specific score: 3 or 4

*One score to be selected for each patient at each evaluation.

APPENDIX 3. Visual scoring system for erythematotelangiectatic rosacea, a secondary endpoint. 0=none, 1=mild (panel A), 2=moderate (panel B), and 3=severe (panel C). Top table reproduced from Sanchez *et al.*, 2005; bottom figure reproduced from Wilkin *et al.*, 2004.

Table II. Clinician's Erythema Assessment Scale*

Score/Grade	Definition
(0) None	No redness present
(1) Mild	Slight pinkness
(2) Moderate	Definite redness
(3) Significant	Marked erythema

Appendix 4. Rosacea quality of life survey derived from Nicholson *et al.*, 2007. The response choices for the questions below are as follows: 1=never, 2=rarely, 3=sometimes, 4=often, 5=all the time. The items below are reliable and have good discriminant ability.

RosaQoL items

1. I worry that my rosacea may be serious
 2. My rosacea burns or stings
 3. I worry about getting scars from my rosacea
 4. I worry that my rosacea may get worse
 5. I worry about side effects from rosacea medications
 6. My rosacea is irritated
 7. I am embarrassed by my rosacea
 8. I am frustrated by my rosacea
 9. My rosacea makes my skin sensitive
 10. I am annoyed by my rosacea
 11. I am bothered by the appearance of my skin (redness, blotchiness)
 12. My rosacea makes me feel self-conscious
 13. I try to cover up my rosacea (with makeup)
 14. I am bothered by persistence/reoccurrence of my rosacea
 15. I avoid certain foods or drinks because of my rosacea
 16. My skin feels bumpy (uneven, not smooth, irregular)
 17. My skin flushes
 18. My skin gets irritated easily (cosmetics, aftershaves, cleansers)
 19. My eyes bother me (feel dry or gritty)
 20. I think about my rosacea
 21. I avoid certain environments (heat, humidity, cold) because of my rosacea
-

10. Safety monitoring and reporting

Serious adverse events, drug misuse or abuse, reports of drug exposure during pregnancy, and any other information that may suggest a change in the benefit-risk profile of secukinumab, and where required, copies of the Investigator Notifications for suspected unexpected serious adverse events (SUSAR) and copies of the Development Safety Update Report, as appropriate.

We will perform an adverse event reconciliation between the Sponsor's trial database and an output from the Novartis safety database periodically throughout the trial.

11. Statistical methods and Data analysis

This study is powered for the primary endpoint of significant reduction of papule/pustule count at baseline versus week 16.

The null hypothesis is that there will be no difference in papule/pustule count at baseline and after 16 weeks of secukinumab due to known chronic and incurable nature of rosacea and that when used for psoriasis, maximum therapeutic effect is seen at 16 weeks. Because of the risk profile of the study medication in suppressing the immune system, we estimate that any reduction in papule/pustule count less than 20% would not be clinically meaningful. Since 10 papules/pustules are required to enroll, the difference in papule/pustule count would have to be at least 2 (assuming a standard deviation of 3). Using an $\alpha=0.05$ and power=0.80 (two sided test), sample size needed is 20.

Assuming a dropout rate of 20% from 20 patients, we would need to enroll **24** patients to achieve sufficient sample size. This is consistent with a study by Sanchez *et al.*, 2005 for oral doxycycline in which 20 individuals were enrolled and achieved statistical significance. (Calculation by [name], MS, Stanford Dermatology biostatistician)

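### As extracted, Appendix 2 gives grades 3 and 4 one erythema guideline and totals 11-15 no grade; separately, secondary endpoint 3 names area while its printed scale grades intensity

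*Combined protocol and SAP*

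**What the plan says.** Section III defines secondary endpoint 2 as the change in a composite global assessment scored with Appendix 2. Table I there has five grades, each with a verbal definition and a guideline made of a lesion count, an erythema total and an area-specific erythema score. Three guideline cells matter most:

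- Grade 2 (Moderate): "10-14 papules/pustules Erythema Assessment Score Total score 6-10; Area-specific score: 2 or 3"
- Grade 3 (Severe): "15-19 papules/pustules Erythema Assessment Score Total score 16-20; Area-specific score: 3 or 4"
- Grade 4 (Very severe): ">20 papules/pustules Erythema Assessment Score Total score 16-20; Area-specific score: 3 or 4"

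The verbal definitions of the last two differ: "Severe erythema; papules/pustules common" for grade 3 and "Fiery red erythema; numerous papules/pustules" for grade 4. The footnote asks for a single grade: "One score to be selected for each patient at each evaluation". The appendix title reads "Clinical score for assessing rosacea severity, reproduced from" a cited study, so the table is presented as a copy.

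Section III words secondary endpoint 3 as a change in the area of facial erythema from before treatment to week 16, read by a blinded, independent photographic assessor with the visual scale of Appendix 3. The printed steps of that scale run from no redness, through "Slight pinkness" and definite redness, to marked erythema, scored 0 to 3. Secondary objective 3 and Section IV speak only of erythema, without saying extent or intensity.

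**The concern.** A grading table used for a change score should send each patient to one grade. On erythema, Table I as extracted points to two grades for totals 16-20 and to none for 11-15. The upper part of the table is the part in use at entry: Section V requires at least ten lesions, so by count every patient enters at grade 2 or above. Where the erythema component decides the grade, two raters, or one rater at two visits, could place the same findings differently. Section 11 gives no scoring rule for this endpoint. The study is open label, and Section IV assigns the blinded reader lesion count and erythema without mentioning the global score.

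For secondary endpoint 3, what is at stake is what may be claimed. A fall on a redness-intensity scale, reported under the endpoint's present wording, would be read as a smaller area of redness.

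**Working it through.** No sample-size or power figure bears on this point, so there is no stated result to reproduce. The check is to take each value in turn and list every grade whose printed band contains it.

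**Inputs (Appendix 2, Table I, as extracted).** Erythema totals: grade 0, <1; grade 1, <5; grade 2, 6-10; grades 3 and 4, 16-20. Area-specific scores: grades 0 and 1, 0 or 1; grade 2, 2 or 3; grades 3 and 4, 3 or 4. Lesion counts: 0-3, 4-9, 10-14, 15-19, >20.

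**Erythema totals 0 to 20**

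| Total | Grades that fit | Number of totals |
|---|---|---|
| 0 | 0 and 1 | 1 |
| 1-4 | 1 | 4 |
| 5 | none | 1 |
| 6-10 | 2 | 5 |
| 11-15 | none | 5 |
| 16-20 | 3 and 4 | 5 |

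Of 21 integer totals, 1 + 5 = 6 have no grade (6/21 = 29%), 1 + 5 = 6 have two, and 4 + 5 = 9 have exactly one. These are shares of possible values, not of patients.

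**Area-specific score.** Scores 0 and 1 fit grades 0 and 1; score 2 fits grade 2; score 3 fits grades 2, 3 and 4; score 4 fits grades 3 and 4. So the overlap also reaches grade 2.

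**Lesion count.** Each count fits one grade, except that exactly 20 fits none.

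**Which results depend on a printed sign.** The gaps at total 5 and count 20 depend on <5 and >20 being printed as such; if the page has ≤5 and ≥20, both disappear. The faults at 11-15 and 16-20 involve no sign.

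**What separates grades 3 and 4 at totals 16-20.** Count does (15-19 against >20), and so does the wording (severe against fiery red). At a count of exactly 20 only the wording is left. When components disagree, for example a count of 12 (grade 2) with a total of 18 (grade 3 or 4), no printed rule says which governs.

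**Would changing one cell be enough?** Suppose, for illustration only, that grade 3 read 11-15; the documents do not say so. Totals 11-15 would then fit grade 3 alone and 16-20 grade 4 alone. Total 5 and count 20 would still have no band, total 0 would still have two, and area-specific score 3 would still fit three grades.

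**Can these totals occur?** The documents do not say how the total is formed. If it is a sum of area scores (assumption), the maxima are:

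| Areas | Scored 0-3 | Scored 0-4 |
|---|---|---|
| 4 | 12 | 16 |
| 5 | 15 | 20 |
| 6 | 18 | 24 |
| 7 | 21 | 28 |

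With 0-4 scoring, four areas reach all of 11-15 and five reach all of 16-20. With 0-3 scoring, the printed range of Appendix 3, five areas reach all of 11-15 but none of 16-20, and seven are needed for all of 16-20.

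**Ceiling on gradings.** A change from baseline to one visit uses at most 24 × 2 = 48 gradings, or 20 × 2 = 40 for the 20 patients needed after dropout. These count all gradings; how many are affected cannot be derived.

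**Secondary endpoint 3.** Set side by side, the endpoint names extent, while all four printed definitions in Appendix 3 describe how red the skin is. None refers to a proportion or region of the face.

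**The case against.** The strongest reply is that the fault may not be in the protocol at all. The table was read from a PDF by a program and is presented as a copy of a published one. Grades 3 and 4 have identical guideline text after the lesion count, which is what a repeated line would look like. This stands in part. The two cells differ in lesion count, so a whole cell was not simply duplicated, but a misread figure or a slip in the source remains possible. The original page has to be checked first.

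Second, the column is headed as a guideline, and count and wording remain available to the grader. This stands, and it limits the point to ambiguity.

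A reader might go further and infer that the same patient's change could be recorded anywhere from 0 to -2. For a fall in total from 18 to 13, baseline grade 3 or 4 and follow-up grade 2 or 3 do give 0, -1 or -2. But that needs lesion count and verbal definition to be ignored, and 11-15 to be placed in a neighbouring grade. Table I does not grade that way, so this is not an estimate of error.

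Third, on secondary endpoint 3, a reader might infer that extent cannot be measured and that only intensity can ever be reported. That also goes too far. Table I refers to area-specific and total erythema scores, and a sum over areas would partly reflect extent. The Appendix 3 figure and the text behind the Table II asterisk are not in the extract and could describe facial areas. What stands is narrower: the printed definitions grade intensity, and no derivation of an area or total score is shown.

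**Conclusion.** The point holds for the text as extracted, and should be fixed. Table I gives grades 3 and 4 the same erythema guideline and gives totals 11-15 no grade. If the signs are as printed, total 5 and a count of exactly 20 are also unplaced. The global score is ambiguous, not unusable. Secondary endpoint 3 names area where its printed instrument grades intensity.

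Only secondary endpoints 2 and 3 are touched; the primary lesion-count endpoint and the sample size are not. No bias or error rate can be put on it, because neither the distribution of erythema totals nor the way the total is formed is given. Confidence is high about what the extract shows, but not about whether the fault lies in the protocol page, its source or the extraction.

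**What to change.** Before any scoring:

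1. Compare Table I with the original protocol page and with the source it says it reproduces. On the same pass, confirm the signs at <1, <5 and >20, and whether the erythema scale has a step 4: Table I uses area-specific scores up to 4, while Appendix 3 as printed stops at 3. Correct any miscopied cell. For gaps or overlaps that remain, or if the source prints the same bands, state one scoring rule that assigns every erythema total and every lesion count to exactly one grade, and say which component governs when count and erythema disagree.
2. Reword secondary endpoint 3 as change from baseline to week 16 in the Appendix 3 erythema severity score, read by the same blinded photographic assessor. State whether it is one whole-face score or a total over named facial areas, and do not report it as change in area.

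The cost is a table check, one scoring rule and one reworded secondary endpoint, with no new visits, readers, procedures or patients. The only loss is that endpoint 3 no longer claims to describe extent.

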This is an open label single arm study whose primary objective is to assess whether secukinumab can significantly reduce the number of papule/pustules after 16 weeks of use. After Stanford Human Subjects Panel approval and written Informed Consent, study participants will use secukinumab 300 mg weekly x 5 weeks (Dose at Week 0, 1, 2, 3, and 4) followed by 2 additional monthly injections (a total of seven 300mg doses), according to the Visit Table. Adverse events will be graded and recorded according to Common Terminology Criteria for Adverse Events (CTCAE) Version 4.0. To avoid investigator bias, a board certified dermatologist blinded to the before or after status of the participant will assess the facial photographs for papulopustule count and erythema. As this is not a crossover study, participants are certainly at risk for reporting bias, however, future larger studies may address this issue. (Because rosacea takes at least 16 weeks to reach maximal clinical response, a crossover study with washout between treatment intervals would be estimated to take 28 weeks, which is a long duration for an exploratory study.) Study participants will follow the procedures as outlined in the Visit Table. Our team has experience administering rosacea quality of life surveys (Chang *et al.*, 2012).

Biomarkers for response such as type and degree of inflammatory infiltrate before and after treatment (16 weeks) will be assessed from 4 mm Keyes punch biopsies of rosacea papules. The tissue will be fixed in formalin and embedded in paraffin for staining with hematoxylin and eosin. Histological assessments will be made by a dermatopathologist blinded to the before or after treatment status of the tissue assessed. Severity of inflammation will be assessed using a 5 point Likert scale, and the numbers of neutrophils, lymphocytes and Langerhans cells will be assessed in a high powered field.

V. Patient population

Adults (N=24) with moderate or severe papulopustular rosacea who meet the eligibility criteria as outlined below.

Key inclusion criteria

- 1) *Moderate to severe papulopustular rosacea defined clinically using the grading system of Wilkin et al. (2004) as having at least ten lesions (either papules or pustules) on face at time of enrollment*
- 2) *Age 18 years or greater*
- 3) *Willing and able to understand and sign informed consent form*

Key exclusion criteria

- 1) *Known hypersensitivity to secukinumab*

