- 2) *Topical or oral anti-rosacea medication usage for 28 days prior to enrollment*
- 3) *Active Crohn's disease, as secukinumab may exacerbate this disease*

- 4) *Active infection including tuberculosis, hepatitis B or C, human immunodeficiency virus*
- 5) *Participants with latent tuberculosis will need to have treatment initiated prior to starting study drug*
- 6) *Pregnant or lactating*
- 7) *Active and/or uncontrolled medical conditions that may interfere with study procedures or obscure rosacea assessment such as cutaneous lupus*
- 8) *Use of retinoids within past 4 weeks of enrollment.*
 - a. *Use of topical retinoids within past 3 months of enrollment is allowed if the regimen is stable for 1 month prior to enrollment and subject agrees to keep regimen unchanged for duration of study*
- 9) *Use of antibiotics within 4 weeks of enrollment*
- 10) *Use of light based or laser treatment to face within 8 weeks of enrollment*
- 11) *Use of systemic steroids within 4 weeks of enrollment*
 - a. *Use of topical steroids is allowed if the regimen is unchanged for 2 weeks prior to enrollment and is unchanged for the duration of the study*
- 12) *Acne conglobate, acne fulminans, chloracne, severe acne requiring systemic treatment*

VI. Treatment

This is an open label study using secukinumab 300 mg subcutaneously weekly x5 weeks (Dose at Week 0, 1, 2, 3, and 4) then monthly x2 months (a total of seven doses of 300mg).

VII. Drug administration

Subcutaneous injection

VIII. Dosing guidelines

This study will use a flat dose that is the FDA approved dose for psoriasis (see Package Insert)

IX. Visit schedule and Assessments

Visit 1 (Week -4 to Baseline)

Following written informed consent, a past medical history, concomitant medications, and physical examination will be performed. Vitals signs will be taken and peripheral blood draw will be performed to assess for blood counts, kidney function, and tuberculosis exposure (See Study Calendar).

Visit 2 Week 0 (Baseline)

After verification of eligibility, participants will undergo vital signs, physical examination, adverse event determination, concomitant medication review, photography, skin biopsy and questionnaire administration. Biopsy will be sent for histology and immunohistochemistry. Study drug will be dispensed with a study diary and instructions on self administration.

Visit 3 Week 4

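### Does the plan need a Week 16 estimate set against its own 20% bar for a worthwhile reduction?

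*Combined protocol and SAP*

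**What the plan says.** Section 11 justifies the bar by the drug's immunosuppressive risk: "we estimate that any reduction in papule/pustule count less than 20% would not be clinically meaningful". It then turns the percentage into a count: "Since 10 papules/pustules are required to enroll, the difference in papule/pustule count would have to be at least 2". With an assumed SD of 3, two-sided alpha of 0.05 and power of 0.80, it arrives at 20 patients, and it enrols 24 to allow for dropout.

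The hypothesis concerns zero change: "The null hypothesis is that there will be no difference in papule/pustule count at baseline and after 16 weeks of secukinumab". Section III and Section IV word the primary objective as a reduction in count after 16 weeks and name no size of effect. The only lesion-count endpoint written as a change (secondary endpoint 1) is absolute and at Week 12.

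Entry requires "having at least ten lesions (either papules or pustules) on face at time of enrollment", with no upper limit. Section V describes the population as "Adults (N=24) with moderate or severe papulopustular rosacea", and Appendix 1 grades 15 or more lesions as severe.

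**The concern.** The bar reads as a benefit-risk statement about how to judge the result, yet after the sample size calculation it is not used again. No Week 16 percent reduction, interval, responder proportion or comparison with 20% is planned. Two lesions cannot stand in for the bar when the result is read, because 2 is 20% only at a baseline of 10. At a baseline of 15 the bar is 0.20 x 15 = 3 lesions.

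At stake is interpretation. A significant reduction smaller than the sponsor's own standard might be presented as a clinical success, and any percent summary chosen after seeing the data would be post hoc.

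**Working it through.** **Inputs.** From Section 11: difference 2, SD 3, two-sided alpha 0.05, power 0.80, n = 20 evaluable, 24 enrolled. Assumption: 3 is the SD of within-patient change. The text does not say so, but this reading reproduces the stated n. Mean baseline is not given, so 10 (entry minimum) and 15 (lowest severe count in Appendix 1) are used as illustrations.

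**1. The plan's own figure.** For a paired t-test on change, noncentral t, difference 2 and SD 3, power is 0.785 at n = 19 and 0.807 at n = 20. So n = 20 is reproduced. Reading 3 as the SD at each visit with zero correlation would need 38.

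**2. Smallest significant mean drop** = t(0.975, n-1) x SD / sqrt(n).
- n = 20: 2.093 x 3/sqrt(20) = 2.093 x 0.671 = 1.40 lesions; 1.40/10 = 14.0%, and 1.40/15 = 9.4%.
- n = 24: 2.069 x 3/sqrt(24) = 2.069 x 0.612 = 1.27 lesions; 1.27/10 = 12.7%, and 1.27/15 = 8.4%.

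**3. Dependence on SD (n = 20, baseline 10).** The same formula gives:

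| SD of change | Smallest significant drop | Percent of 10 |
|---|---|---|
| 2 | 0.94 | 9.4% |
| 3 | 1.40 | 14.0% |
| 4 | 1.87 | 18.7% |
| 5 | 2.34 | 23.4% |

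**4. Chance of a significant result with an estimate below 20%** (n = 20; simulated normal mean change and chi-square variance; mean baseline treated as fixed):

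| True reduction | Baseline 10, SD 3 | Baseline 15, SD 3 |
|---|---|---|
| 15% | 0.34 | 0.76 |
| 20% | 0.31 | 0.49 |
| 25% | 0.17 | 0.13 |
| 30% | 0.06 | 0.01 |

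Only the ratio of SD to baseline matters. Baseline 15 with SD 4.5 (ratio 0.3) gives the baseline 10, SD 3 column. At ratio 0.4 (SD 6 at 15, or SD 4 at 10) the chance is at most about 0.09. At ratio 0.5 (SD 5 at 10) it is at most about 0.014. At baseline 10 and SD 3 it is 0.001 if the true reduction is 40%.

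**5. Does planning at a baseline of 10 harm power?** No. A 20% drop from 15 is 3 lesions, with power 0.989 if the SD stays 3 and 0.807 if it scales to 4.5.

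**6. What an interval would add.** At n = 20 and SD 3 the 95% half-width is 1.40 lesions. An observed mean drop of 2 gives 2 - 1.40 = 0.60 to 2 + 1.40 = 3.40, or 6% to 34% of a baseline of 10. An observed reduction at the bar could be neither confirmed nor ruled out as meeting it. If the lower limit had to exceed 2 lesions, a true mean drop of 3 would need 73 patients.

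**The case for a change.** The best case for a change is that it costs almost nothing. The bar has a clinical reason behind it, significance is the only criterion in Section 11, and a percentage worked out from two reported means carries no interval. How the percentage is formed can also matter. Suppose 19 patients go from 12 to 9 and one goes from 3 to 6. The mean of individual reductions is (19 x 25 - 100)/20 = 18.75%, while mean change over mean baseline is 54/231 = 23.4%. Low analysed baselines are possible: under Section IV the assessor is "blinded to the before or after status of the participant will assess the facial photographs for papulopustule count and erythema", and Section IX puts that photography after eligibility is verified.

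The factual part stands: no Week 16 percent estimate is planned, and choosing one in advance would be tidier. The rest carries less weight. A photographic baseline of 3 in a patient who entered with at least ten lesions is an extreme case. The documents do not say whether 20% applies to the group mean or to each patient, so no single percent measure follows from the text. The planned test also gives no wrong answer to the question it is set.

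**Conclusion.** No change is needed. The test against zero answers the primary objective, and 20 patients is correct on the stated inputs. The 20% figure serves as a smallest worthwhile difference for sizing, and the plan never says that significance establishes clinical benefit. For a study that calls itself proof-of-concept and exploratory, leaving an effect-size decision rule out is a fair choice. The missing mean and percent change are a reporting gap that analysts can fill from data already collected.

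The size of the issue rests on assumptions the documents do not settle: that 3 is the SD of change, and the mean baseline. With SD 3 and n = 20, significance can be reached at 14.0% of a baseline of 10, and the chance of a significant estimate below the bar is 0.34 to 0.06 for true reductions of 15% to 30%. It is higher at a baseline of 15 with SD 3 when the true reduction is 20% or less. At baseline 10 with SD 5 the concern largely disappears. If a percent reduction is reported, it is best read descriptively. For the ratio of mean change to mean baseline, Fieller's interval (simulated coverage about 95%) is a better choice at this sample size than a percentile bootstrap (about 92% to 93%).

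### Minor: 24 enrolled patients give 20 completers only if dropout is at most 16.7%, not the stated 20%, because the allowance was taken on the 20 needed (20 + 4) rather than on those enrolled (20/0.80 = 25)

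*Combined protocol and SAP*

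**What the plan says.** The sample-size argument is in section 11 (Statistical methods and Data analysis). It takes a 20% reduction from the 10 lesions required for entry, so "the difference in papule/pustule count would have to be at least 2", "assuming a standard deviation of 3". With two-sided alpha 0.05 it concludes "power=0.80 (two sided test), sample size needed is 20".

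The dropout step follows: "Assuming a dropout rate of 20% from 20 patients, we would need to enroll" 24 "patients to achieve sufficient sample size". Section V (Patient population) carries the same enrolment target: "Adults (N=24) with moderate or severe papulopustular rosacea".

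Section 11 does not name the test, and does not say whether the SD of 3 belongs to the counts or to the change within a patient. The document gives no rule for replacing patients who leave, no rule for missing week 16 counts and no definition of an analysis set.

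**The concern.** The 20 is the number of patients the plan needs for the baseline to week 16 comparison. A dropout rate normally describes the share of enrolled patients who are lost, so the required number has to be divided by one minus the rate. The plan instead multiplies the required number by one plus the rate. This always gives too small an enrolment, because the extra patients can also drop out.

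What is at stake is the single statement that 24 is enough under the named dropout rate. A reader would take it that the trial can lose a fifth of its patients and still have 20 to analyse, which is not so.

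**Working it through.** **Inputs, all from section 11 except where noted**

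- Difference: 2 lesions (20% of 10)
- SD: 3
- Two-sided alpha 0.05, power 0.80
- Patients needed: 20
- Dropout: 20%, applied to those 20
- Enrolment: 24 (also section V)

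**Step 1: reproduce the 20.** Assume a paired t-test with an SD of the change of 3, so the standardised difference is 2/3. The noncentrality parameter is (2/3)√n with n − 1 degrees of freedom.

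| n | Power, paired t | Power, normal approximation |
|---|---|---|
| 17 | 73.3% | 78.5% |
| 18 | 76.0% | 80.7% |
| 19 | 78.5% | 82.8% |
| 20 | 80.7% | 84.6% |

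The paired t-test gives 20 as the smallest n with at least 80% power, so this reading matches the plan. The normal approximation needs only (3 × (1.960 + 0.842)/2)² = 17.7, that is 18, and does not match.

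**Step 2: reproduce the 24.** 20 × (1 + 0.20) = 24, exactly the stated figure.

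**Step 3: apply the rate to those enrolled.**

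- Enrolment needed: 20/(1 − 0.20) = 25
- Expected completers from 24: 24 × 0.80 = 19.2
- Largest loss from 24 that leaves 20: 4/24 = 16.7%
- In whole patients: 5 lost of 24 is 20.8% and leaves 19; 5 lost of 25 is 20.0% and leaves 20

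None of Step 3 depends on the test or on the SD.

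**Step 4: effect on power.** On the Step 1 reading, going from 20 to 19 completers costs 80.7 − 78.5 = 2.2 percentage points. To put that in proportion, with the same test and other assumed SDs of the change:

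| SD of change | n = 19 | n = 20 |
|---|---|---|
| 2.8 | 83.7% | 85.8% |
| 3.0 | 78.5% | 80.7% |
| 3.2 | 73.1% | 75.5% |

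If 3 is instead the SD of the counts, the SD of the change is 3√(2(1 − ρ)), where ρ is the correlation between baseline and week 16. The document gives no ρ. For assumed values of 0, 0.25, 0.5 and 0.75, power at 19 completers is 49.4%, 61.2%, 78.5% and 97.3%. At 20 completers it is 51.6%, 63.7%, 80.7% and 97.9%. In every row the lost patient matters far less than the SD.

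**The case against.** The strongest reply is that the plan discloses its base. It says the 20% is taken from 20 patients; that is 4 patients, and 24 − 4 = 20. On those words the sum is consistent, and it becomes wrong only under the usual convention that a dropout rate refers to those enrolled. This explains where 24 came from. It does not make 24 sufficient when a fifth of the enrolled patients leave, which is what a reader will understand.

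The second reply is that the effect is close to nil, and this stands. The expected shortfall is 20 − 19.2 = 0.8 of a patient. Enrolling 25 would not guarantee 20 either: if each patient drops out independently with probability 0.20 (an assumption), the chance of at least 20 completers is 0.46 with 24 enrolled and 0.62 with 25. Averaged over that dropout, paired t power is 78.5% with 24 and 80.3% with 25.

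The third reply is that the power figures assume only completers are analysed. Lesions are also assessed at weeks 4 and 12, so an analysis using those visits could recover some information. If all 24 could be used with the same difference and SD, which is optimistic, power would be 87.8%. This is a fair limit on the power figures, but the plan describes no such analysis, and the count of completers is unaffected. The SD scenarios concern a separate ambiguity and are given only for scale.

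**Conclusion.** The point holds, at the lowest level of importance. The dropout allowance uses the wrong base: 24 enrolled protects the required 20 for dropout up to 16.7% of those enrolled, and at the stated 20% about 19 complete. That shortfall of one patient follows from the plan's own figures alone.

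The fall in power from 80.7% to 78.5% is conditional on a paired t-test, an SD of change of 3 and an analysis of completers. Under a normal approximation, power with 19 stays above 80%. Section IV describes the work as exploratory ("which is a long duration for an exploratory study"), and the conclusion about the drug would be reached in the same way with 19 patients as with 20. The target of 24 in section V is only an enrolment number and can stand; what needs correcting is the justification for it in section 11.

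**What to change.** Keep 24 and replace the dropout sentence in section 11 with wording such as:

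> 24 enrolled gives 20 completers for dropout up to 16.7% of those enrolled; at 20% dropout about 19 complete.

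Only if the sponsor confirms that the calculation used a paired t-test with an SD of change of 3, add:

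> Power is about 81% with 20 completers and about 78% with 19.

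The cost is one sentence and a slightly less favourable stated figure. No patients are added and the analysis does not change.
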